7.2.4.2. Demography and Baseline Characteristics

The following will be recorded on the CRF for each subject:

- Age: Record the age of the subject at the time of enrollment. The age should be calculated by the date of birth.
- Purpose of treatment: Between 'treatment for moderate to severe vasomotor symptoms associated with menopause' and 'prevention of post-menopausal osteoporosis', select one that is applicable, but both can be selected.
- Presence and characteristics of the vasomotor symptoms associated with menopause: Select 'Yes' or 'No'. If 'Yes' is selected, select 'moderate' or 'severe' for the severity and record the duration of the disease (years/months).
- Other past/present diseases: Past or present diseases (including liver disorder and renal disorder) will be determined based on the date of the first dose of Duavive tab. Record 'Yes' or 'No'. If 'Yes', record the adequate full name of the disease as specified in the Medical Terminology Dictionary (published by the Korean Medical Society), and indicate whether it is 'Past disease' or 'Present disease'. 'Past disease' refers to a disease occurred in the past of which the condition has been recovered by the time of the administration of Duavive tab., whereas 'Present disease' refers to a disease that is present at the time of the first administration of Duavive tab.
- Allergic history: Record the history of all allergies.

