3 INTERIM AND FINAL ANALYSES

This Statistical Analysis Plan (SAP) details the analyses and outputs to be produced for the interim and final analyses.

For the first 2 years, 6-month reports will be submitted to the MFDS (i.e., Reports 1-1, 1-2, 2-1, and 2-2). Thereafter, data collected in the 3rd, 4th, and 5th year will be reported to the MFDS annually. The final study report (i.e., re-examination report) will be submitted to the MFDS in the 6th year to include all data collected during the whole study period. The first interim analysis will be performed once this SAP is finalized.

All analyses outlined in this SAP, except for those described below, will be performed for each interim analysis for the periodic report annually.

- Type of medical history (Past disease, Present disease)
- Type of concomitant medications
- Type of Hormone therapy related to menopause before administration of Duavive Tab.
- SAE/SADR, unexpected AE/unexpected ADR by preferred terms according to the frequency categories in the approved local label
- Basic Results Tables

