8.1.2 Analysis for Categorical Data

Descriptive statistics for categorical variables will be given as frequencies and percentages. The denominator will be the number of subjects included either in the safety analysis set or effectiveness analysis set depending on where the analysis is presented.

Where appropriate, the percentages will be presented with a corresponding 95% confidence interval. Comparisons between subcategories of each baseline characteristic will be made using chi-square test or Fisher's exact test. Test statistics include p-value. When more than 20% of expected frequency of the cell count is less than 5, Fisher's exact test should be used instead of chi-square test.

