8.2 STATISTICAL ANALYSES

8.2.1 Safety Analyses

8.2.1.1 Baseline Characteristics

Baseline characteristics for this study are defined as follows:

- Continuous measurements will be presented Mean (SD) :
 - Age
 - Duration of disease[†]
 - Total administration period of Duavive tab.[‡]
- Categorized measurements will be presented n(%) :
 - Main indication (Treatment for moderate to severe vasomotor symptoms associated with menopause, Prevention of post-menopausal osteoporosis, both)
 - Geriatric status (<65 years, ≥65 years)
 - Age (<50 years, ≥50 years and ≤59 years, ≥60 years and ≤69 years, ≥70 years*)
 - Allergy history (Yes, No)
 - Duration of disease[†] (<3 months, ≥3 months and <6 months, ≥6 months*)
 - Medical history (Past disease, Present disease/Yes, No)
 - Total administration period of Duavive tab. (<3 months, ≥3 months and <6 months, ≥6 months*)
 - Long-term administration (<22 weeks, ≥22 weeks of total administration period of Duavive tab.)
 - Kidney disorder (Yes, No)
 - Liver disorder (Yes, No)
 - Concomitant medication (Yes, No)
 - Hormone therapy related to menopause before administration of Duavive Tab. (Yes, No)

[†] Only if main indication is “Treatment for moderate to severe vasomotor symptoms associated with menopause”

Duration of disease (months) = (number of years after diagnosis)×12+(number of months after diagnosis)

[‡] Total administration period of Duavive tab.= Sum of each administration period

: Each administration period = (Administration end date) – (Administration start date) + 1

If the medication is being continued at the completion of the study, administration end date is replaced with effectiveness evaluation date at last visit.

* The categories can be altered depending on the data distribution.

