8.2.1.3 Adverse Events by Baseline Characteristics

The following will be presented for AEs, split by the baseline characteristics using the safety analysis set:

- The number of subjects to whom AE occurred and the number of AEs will be calculated.
- The proportion of subjects to whom AE occurred and its 95% confidence interval will be estimated and compared between subcategories of each baseline characteristic using chi-square test or Fisher's exact test. When more than 20% of expected frequency of the cell count is less than 5, Fisher's exact test should be used instead of chi-square test.
- Adverse event presentations will be split by the following baseline characteristics (See Categorized measurements of Section 8.2.1.1)

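### The SAP lets the bands of three ordered factors be changed without a rule and tests them only with order-blind tests; add a count-based merging rule and a trend test beside the existing one

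*SAP*

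**What the plan says.** SAP 8.2.1.1 sets the age bands as "Age (<50 years, ≥50 years and ≤59 years, ≥60 years and ≤69 years, ≥70 years". Duration of disease (vasomotor indication only) and total administration period each use "<3 months, ≥3 months and <6 months, ≥6 months". All three carry an asterisk leading to the note "The categories can be altered depending on the data distribution". Geriatric status (split at 65 years) and long-term administration (split at 22 weeks) carry no asterisk.

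Age and duration exist as numbers. Protocol 7.2.4.2 derives age from date of birth, and its instruction on vasomotor symptoms reads "for the severity and record the duration of the disease (years/months". SAP 8.2.1.1 converts duration to months. In numeric form they are only summarised: "Continuous measurements will be presented Mean (SD".

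For testing, SAP 8.1.2 says "Comparisons between subcategories of each baseline characteristic will be made using chi-square test or Fisher's exact test". SAP 8.2.1.3 applies this to adverse events, which are "compared between subcategories of each baseline characteristic using chi-square test" or Fisher's test, and SAP 8.2.2 does the same for effectiveness in each indication. Neither document contains a trend test or a regression.

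On timing, SAP section 3 says that all analyses outside a short list of exceptions "will be performed for each interim analysis for the periodic report annually". The splits by baseline characteristic are not on that list.

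**The concern.** The second of the two study objectives is to identify factors that affect safety and efficacy, and these subgroup tests are the only inferential tool given for it. Two features weaken them.

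- **Open cut-points.** The study is open-label, and outcomes by band appear in annual reports planned for 2017, 2018 and 2019, before the re-examination report of October 2020. A band altered for the final report could therefore be altered by someone who has seen how outcomes fall across bands. The SAP has no wording that excludes this, so a reader of the report could not tell a harmless merge from a chosen one.
- **Order ignored.** Age with four bands is tested on 3 degrees of freedom, and the other two factors on 2. If risk rises or falls steadily, a 1-degree-of-freedom test is more likely to find it. The 600 women are a regulatory minimum with no power calculation behind it, so spare power cannot be assumed.

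**Working it through.** The plan states no power or effect size for these comparisons, so there is no figure to reproduce.

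**From the documents:** N = 600 (Protocol 7.5), two-sided 0.05 (SAP 8.1), and the bands quoted above. **Assumed:** adverse event rates, age mixes and odds ratios (OR), as stated at each step.

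**1. Power for a steady trend.** Let w be the band shares, p the event risks, p̄ = Σwp, s = 0, 1, 2, … the band scores and s̄ = Σws. The non-centrality is

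- general test (k−1 df): N Σw(p−p̄)² / [p̄(1−p̄)]
- Cochran-Armitage trend test (1 df): N [Σw(s−s̄)(p−p̄)]² / [Σw(s−s̄)² · p̄(1−p̄)]

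Example: age mix 20/50/23/7%, 15% in the youngest band, OR 1.3 per band. Risks are 15.0, 18.7, 23.0 and 27.9%, so p̄ = 19.6%. The non-centralities are 4.63 (general) and 4.60 (trend), almost equal. The critical values are 7.81 (3 df) and 3.84 (1 df), so power is 41% against 57%.

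| Age mix | OR per band | General | Trend | Difference |
|---|---|---|---|---|
| 20/50/23/7% | 1.3 | 41% | 57% | 16 |
| 20/50/23/7% | 1.4 | 66% | 81% | 15 |
| 20/50/23/7% | 1.5 | 85% | 94% | 9 |
| 20/60/20% (top band merged) | 1.3 | 27% | 35% | 8 |
| 20/60/20% | 1.4 | 44% | 54% | 10 |
| 20/60/20% | 1.5 | 62% | 72% | 10 |

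For duration of disease, with equal thirds, OR 1.5 and all 600 women, the figures are 56% against 66% at an overall event rate of 10%, and 82% against 89% at 20%. Fewer than 600 women may have that indication, which would lower both.

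Using age as a number gains more. With age simulated as normal (mean 55, SD 6), a 20% event rate at age 55 and OR 1.6 per 10 years, power is 56% (general), 69% (trend) and 79% (continuous).

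**2. The reverse case.** With shares 20/50/23/7% and U-shaped risks of 25/15/15/25%, the general test has 66% power and the trend test 13%. With shares 20/55/20/5% and risks 25/15/25/15%, the figures are 73% and 6%.

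**3. Worst case for open cut-points.** Data were simulated with no true effect, 600 women, a 20% event rate and age normal (55, 6). The smallest p-value over several plausible groupings was taken. Two simulations used different sets of age groupings.

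| Factor | Fixed bands | Best of 3 | Best of 5 | Best of 6 | Best of 8 |
|---|---|---|---|---|---|
| Age | about 5% | 9-12% | 13% | – | 17-19% |
| Duration (log-normal, median 12 months) | 4% | 10% | – | 16% | – |

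**4. Why merging may be needed.** Under that age distribution, P(age ≥70) = P(Z > 15/6) = 0.6%, or about 4 of 600 women. Both cells of that band then have expected counts below 5, which is 2 of 8 cells (25%), and the SAP's 20% rule would switch to Fisher's test. The age simulations used chi-square throughout, so their figures are approximate in this respect.

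**The case against.** **The note means covariate spread.** It stands among the baseline characteristics, its asterisk sits on the top band, and step 4 shows why a sponsor would want to merge a sparse band. This is the natural reading. A reader might infer that the SAP plans results-driven cut-points, or that its false-positive rate is 9-19%. The documents support neither: they list one grouping per factor and nowhere provide for choosing the best p-value. What stands is that the wording leaves the possibility open.

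**The general test is defensible.** A reader might also infer that chi-square is the wrong test and should give way to a trend test. Neither document assumes a monotone effect, and step 2 shows that replacement could lose most of the power for a U-shape. This objection stands in full against replacement. It does not count against adding a second test.

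**The analysis is exploratory.** SAP section 4 marks hypotheses and decision rules as not applicable. Protocol 7.7.2 calls the evaluation mainly descriptive and makes adverse event frequency the primary concern. The fixed 65-year split already gives age one locked comparison. All of this limits the weight of the point, but p-values judged at 0.05 are still produced for the second objective.

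**Conclusion.** The point holds as two modest weaknesses in an exploratory objective. The overall adverse event rate and the effectiveness rates with their confidence intervals are untouched.

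- The freedom to alter bands of age, duration of disease and total administration period has no trigger, timing or safeguard. The 9-19% is a bound on misuse, under the assumed groupings and distributions. It does not describe how the plan will perform.
- The order-blind tests cost roughly 8-16 points of power for a steady age trend at N=600. This assumes 15% events in the youngest group, OR 1.3-1.5 per band and the two age mixes shown. The loss is nearer 8-10 points once a sparse top band is merged. For non-monotone patterns the existing test is the better one.

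**What to change.** In SAP 8.2.1.1, replace the asterisk note for all three factors with a rule:

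- The listed cut-points stand.
- Only adjacent bands may be merged, and only when a band holds fewer than a stated number of women (for example 10).
- The decision uses factor counts alone and applies identically to every outcome.
- Any other change is reported as post hoc.

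In SAP 8.1.2, 8.2.1.3 and 8.2.2, keep the chi-square/Fisher comparison. Beside it, prespecify for the ordered factors a Cochran-Armitage trend test with stated scores, exact when sparse. For age and duration of disease, the alternative is a logistic regression on recorded age and on duration in months, giving the odds ratio with its 95% CI. State which of the two is used.

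The cost is a few lines of SAP text and some programming; no new data are needed. The downside is one extra exploratory p-value per ordered factor. The trend test also has little power for U-shaped patterns, which is why the general test stays.

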8.2.1.2 Adverse Events

All adverse events reported after start of administration of Duavive tab. will be considered as on-treatment and summarised. Adverse events reported with partial dates of onset will be assumed as on-treatment, unless month/year of AE onset date is before start date of Duavive tab.

In the safety analysis set, the number of subjects to whom AE occurred and the number of AEs will be calculated and the incidence rate of AEs will be estimated with its 95% confidence interval.

8.2.1.3 Adverse Events by Baseline Characteristics

The following will be presented for AEs, split by the baseline characteristics using the safety analysis set:

- The number of subjects to whom AE occurred and the number of AEs will be calculated.
- The proportion of subjects to whom AE occurred and its 95% confidence interval will be estimated and compared between subcategories of each baseline characteristic using chi-square test or Fisher's exact test. When more than 20% of expected frequency of the cell count is less than 5, Fisher's exact test should be used instead of chi-square test.
- Adverse event presentations will be split by the following baseline characteristics (See Categorized measurements of Section 8.2.1.1)

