6. OBJECTIVE OF STUDY

In this study, the safety and efficacy of Duavive tab. 0.45 mg/20 mg will be observed under the actual condition of use.

The objectives of this post-marketing surveillance are as follows:

- 1) To observe the safety and efficacy profile of Duavive tab. 0.45 mg/20 mg in the Korean subjects.
- 2) To identify the factors that can have an effect on the safety and efficacy profile of Duavive tab. 0.45 mg/20 mg in the Korean subjects.

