7.7.2. Interpretation Method (Statistical Considerations)

The data collected from each investigator during the re-examination period will be analyzed. The evaluation of data is shown by summarizing the data mainly using descriptive statistics, etc.

Since the frequency of adverse events occurring during the re-examination period is the primary concern of this study, the frequency of each adverse event will be presented at a 95% confidence interval. The status of the onset of serious AEs/ADRs, unexpected AEs/ADRs, and serious and unexpected AEs/ADRs will be summarized in separate tables.

Unexpected AEs/ADRs will be classified by medical review with reference to the local product document. Events already included in the “Precautions for use” section of the local product document will be classified as “expected”. All other events that are not included in the “Precautions for use” section of the local product document will be classified as “unexpected”. The unexpected AEs include any events that may be symptomatically and pathophysiologically related to the events listed in the local product document, but differ from the labeled event because of greater severity or specificity.

Subgroup analysis will be conducted by factor considered necessary including demographics and baseline characteristics to identify the factors having effects on safety and efficacy.

Total number of participating institutions, number of enrolled and collected cases and number of cases included in the analysis will be presented in the summary table.

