8 STATISTICAL METHODOLOGY AND STATISTICAL ANALYSES

8.1 STATISTICAL METHODS

All test statistics will be the results of two-sided tests with the statistical significant level of 0.05.

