8.2.2 Effectiveness Analyses

Final effectiveness will be analyzed based on the evaluation of investigator for clinical response. Effectiveness analyses will be conducted for each indication. Because both indications can be selected, subjects can include in effectiveness analysis in duplicate.

- 1) Treatment for moderate to severe vasomotor symptoms associated with menopause:

Subjects who were assessed as ‘improved’ in “effectiveness evaluation” would be considered as “Effectiveness” and ‘no change’, ‘aggravated’ in “effectiveness evaluation” would be considered as “Ineffectiveness”. The effectiveness rate at last visit, which is defined as the proportion of subjects classified as ‘effectiveness’ in the final effectiveness evaluation, will be estimated with its 95% confidence interval.

For at last visit, the effectiveness rate according to the baseline characteristics listed in categorized measurements of section 8.2.1.1 (except for “Main indication” item) will be analyzed. Chi-square test or Fisher’s exact test will be used for comparing between subcategories of each baseline characteristic. When more than 20% of expected frequency of the cell count is less than 5, Fisher’s exact test should be used instead of chi-square test.

The frequency and percentage of clinical response evaluation at 3 months (± 2 weeks), 6 months (± 2 weeks), last visit (‘Effectiveness (improved)’, ‘Ineffectiveness (no change, aggravated)’ will be summarized.

- 2) Prevention of post-menopausal osteoporosis:

Subjects who were assessed as ‘effective in prevention’ in “effectiveness evaluation” would be considered as “effectiveness” and ‘ineffective in prevention’ in “effectiveness evaluation” would be considered as “ineffectiveness”. The effectiveness rate at last visit, which is defined as the proportion of subjects classified as ‘effectiveness’ in the final effectiveness evaluation, will be estimated with its 95% confidence interval.

For at last visit, the effectiveness rate according to the baseline characteristics listed in categorized measurements of section 8.2.1.1 (except for “Main indication” item) will be analyzed. Chi-square test or Fisher’s exact test will be used for comparing between subcategories of each baseline characteristic. When more than 20% of expected frequency of the cell count is less than 5, Fisher’s exact test should be used instead of chi-square test.

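### Objective 2 rests on about 33 to 36 unadjusted tests at 0.05, so an apparent factor may be confounded or a chance finding

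*SAP*

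**What the plan says.** Protocol section 6 gives two objectives. The second is "To identify the factors that can have an effect on the safety and efficacy profile of Duavive tab". Protocol 7.7.2 assigns the task to subgroup analysis, whose purpose is "to identify the factors having effects on safety and efficacy".

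The SAP implements this as follows:

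- **AEs (SAP 8.2.1.3).** The proportion of women with an AE is shown with a 95% confidence interval and "compared between subcategories of each baseline characteristic using chi-square test or Fisher's exact test". The tables are "split by the following baseline characteristics (See Categorized measurements of Section 8.2.1.1").
- **Effectiveness (SAP 8.2.2).** For each indication, "the effectiveness rate according to the baseline characteristics listed in categorized measurements of section 8.2.1.1" is tested in the same way at the last visit, leaving out main indication.
- **Significance level (SAP 8.1).** "All test statistics will be the results of two-sided tests with the statistical significant level of 0.05".

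Neither document specifies a multivariable model, a stratified analysis, multiplicity control or a rule for interpreting these p-values. SAP section 4, on hypotheses and decision rules, is marked not applicable.

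**The concern.** A one-factor test shows whether two groups differ. It does not show whether the factor is responsible. Several listed characteristics overlap: geriatric status is a cut of age, long-term administration is a cut of total administration period, and kidney disorder is recorded among past and present diseases. Present disease and concomitant medication can be expected to go together. A factor with no effect can therefore look influential because it accompanies one that has an effect.

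The number of tests also makes some chance findings likely. Three features of the SAP add to this:

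- The factor tests are not among the exceptions in SAP section 3, so they recur in the periodic reports.
- SAP 8.2.1.1 lets the categories of age, disease duration and administration period change with the data distribution.
- Administration period and long-term administration are listed as baseline characteristics but are known only after treatment starts. An AE that ends treatment shortens them, so an association can run from outcome to factor.

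At stake is how far a reader can rely on any factor that appears to matter in the re-examination report.

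**Working it through.** The plan states no error rate or power for these tests, so there is no figure to reproduce. The 600 is a regulatory minimum (Protocol 7.5).

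**Step 1: count the tests.** SAP 8.2.1.1 lists 12 categorized items. Disease duration is defined only for the vasomotor indication. The entry "Medical history (Past disease, Present disease/Yes, No") can be read as one test or two.

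| Family | Medical history as one test | Past and present separate |
|---|---|---|
| AEs | 12 | 13 |
| Vasomotor (no main indication) | 11 | 12 |
| Osteoporosis (no main indication or disease duration) | 10 | 11 |
| Total | 33 | 36 |

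The totals become 34 and 37 if disease duration is also tested among osteoporosis women who have both indications.

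**Step 2: chance findings at one analysis, if no factor matters and tests are independent.**

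- Expected number with p<0.05: 33 × 0.05 = 1.65; 36 × 0.05 = 1.80.
- Chance of at least one: 1 − 0.95^33 = 81.6%; 1 − 0.95^36 = 84.2%.
- AE family alone: 1 − 0.95^12 = 46.0%; 1 − 0.95^13 = 48.7%.

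**Step 3: allow for overlap.** I simulated the 36-test plan with no true factor, 600 women and the SAP's switch between chi-square and Fisher (300 runs per scenario; Monte Carlo error about 2.5 points). All of these inputs are assumptions: age mean 56, SD 6; present disease 40%; concomitant medication 70% with present disease and 20% without; past disease 20%; prior hormone therapy 30%; allergy 5%; kidney disorder 2%; liver disorder 1%; AE rate 10%, 20% or 30%; effectiveness 60-80%.

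- At least one p<0.05: 76-77%.
- Mean number: 1.55-1.58.
- At least one in the AE family: 45-47%.

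**Step 4: confounding.** Assume that only present disease (40% of women) affects AE risk, and that concomitant medication has no effect but is commoner with present disease. Under strong correlation (20% versus 70% use):

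- Medicated: 0.6 × 0.20 + 0.4 × 0.70 = 0.40 of women.
- Present disease among medicated: 0.28/0.40 = 70%; among the rest: 0.12/0.60 = 20%.
- With AE risk 10% versus 20%, crude AE rates are 10 + 10 × 0.70 = 17% and 10 + 10 × 0.20 = 12%.

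Share of simulated studies (600 women, 500 runs each) in which the inert factor reached p<0.05:

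| Medication use without / with present disease | AE risk without / with present disease | Unadjusted test | Logistic model with both factors |
|---|---|---|---|
| 20% / 70% | 10% / 20% | 41% | 6% |
| 20% / 70% | 15% / 30% | 60% | 7% |
| 30% / 50% | 10% / 20% | 9% | 4% |
| 30% / 50% | 15% / 30% | 11% | 6% |

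**Step 5: how large a model the data can carry.** At assumed AE rates of 5%, 10%, 20% and 30%, 600 women give 30, 60, 120 and 180 events. Twelve parameters would leave 2.5, 5, 10 and 15 events per parameter. Seven (the AE model under the fix: three-level indication as two, plus five single terms) would leave 4.3, 8.6, 17.1 and 25.7.

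**The case against.** The best defence is that these are descriptive tables. Protocol 7.7.2 says the data are mainly summarized descriptively and names AE frequency as the primary concern. SAP section 4 sets no decision rule, and SAP 8.2.1.3 gives confidence intervals as well as p-values. Protocol 7.9 discloses that the analysis plan follows the regulator's re-examination guidelines. The SAP does what Protocol 7.7.2 asks, so the lack of a model is not a departure from the protocol.

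Much of this stands. A reader might infer that spurious factors will be reported as effects, or that objective 2 goes unanswered. The documents support neither. They do not say how p-values will be worded or turned into conclusions, and subgroup comparison is the tool the protocol names. Formal familywise control is not required either.

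The defence does not remove the point. Purely descriptive tables would need no 0.05 threshold, and the stated purpose is to find factors that have effects. Calling a comparison exploratory deals with multiplicity but not with confounding.

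It is also fair to object that a large adjusted model could do harm. Protocol 7.3.1.1 sends drugs prescribed for an AE to the Concomitant Medications section, so that variable can be a result of the AE. Symptom severity and disease duration exist only for women with vasomotor data. With no imputation (SAP section 7), including them in an AE model would drop osteoporosis-only women. Known liver disease is an exclusion, and violators leave the safety set (SAP 5.1), so that factor may be almost empty. The fix has to respect these limits.

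**Conclusion.** The point holds as a worthwhile improvement. The second objective seeks factors with effects, and the only planned method is 33 to 36 unadjusted tests at 0.05. An apparent factor may therefore be confounded or due to chance.

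The 82-84% chance of at least one false signal is an upper figure that assumes independence. About 76-77% is more realistic, but rests on assumed prevalences and rates. Both are for a single analysis with no true factor. The confounding figures, roughly 10% to 60%, depend on a correlation and risks that the documents do not give. The upper part of that range should not be read as a prediction for this study.

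**What to change.** 1. **Keep the tables in SAP 8.2.1.3 and 8.2.2.** State that their p-values are exploratory and unadjusted, and give the number of tests.
2. **Add a prespecified logistic model for AE occurrence**, using baseline factors available for all subjects: age (continuous), indication, allergy history, present disease at first dose and prior hormone therapy. Include concomitant medication only if it started before the first dose. If the recorded treatment durations do not show this, leave it out.
3. **Add a second logistic model for vasomotor effectiveness**, in vasomotor subjects, with symptom severity and duration as further covariates.
4. **Leave out** administration period, long-term administration and medication started after the first dose, since each can result from an AE. Leave out liver disorder if it is nearly empty.
5. **Limit the covariates to what the events allow**, and use penalised likelihood if events are few. Report adjusted odds ratios with 95% confidence intervals.

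The cost is a few lines of SAP text and two models on data already collected. The downside is imprecise adjusted estimates if events are few, which the intervals will show. I propose no osteoporosis model: that evaluation needs paired test results (Protocol 7.3.2.1), and the documents do not say how many women will have them.
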